6.7.1 Prohibited concomitant therapy

Concomitant treatment with another systemic anticancer therapy or another investigational medicinal product is prohibited throughout the study after enrollment.

Initiation of the following medications during the study treatment period is prohibited:

- Any investigational medicinal product
- Radiopharmaceuticals
- Immunotherapy and immune-oncology agents
- Cytotoxic chemotherapy
- Apalutamide, bicalutamide, flutamide, nilutamide
- Abiraterone acetate, TAK-700, or other CYP17 inhibitors
- LHRH antagonist, LHRH agonist
- Hormonal treatment that is intended for cancer treatment such high dose testosterone. Substitutive hormone treatments are permitted.

For details of drug-drug interactions please refer to USPI for both darolutamide and enzalutamide

6.7.2 Permitted concomitant therapy

In general, concomitant medications and therapies deemed necessary for the supportive care (e.g., such as anti-emetics, anti-diarrhea) and safety of the patient are allowed except those prohibited in Section 6.7.1.

All medication or vaccine (including over-the-counter or prescription medicines, vitamins, and/or herbal supplements) that may affect the efficacy, toxicity or taken for any concurrent medical conditions at the time of enrollment or during the study must be recorded along with:

- Reason for use
- Dates of administration including start and end dates
- Dosage information including dose and frequency

The Medical Monitor should be contacted if there are any questions regarding concomitant or prior therapy.

Page: 50 of 86

Analgesic use will be captured in eCRF. Investigators or designees are to record which opioid and non-opioid medications were used since the last visit, and Investigators or designees are to record exact daily doses of each analgesic consumed.

Participants should be evaluated by investigators for presence of osteoporosis according to local guidelines and be provided with bone treatment support per local standard of care.

Participants receiving treatment with osteoclast-targeted therapy at a dose and schedule indicated for osteoporosis prior to study entry may continue treatment at the same dose and schedule.

6.8 Treatment After the End of the Study

After completion of the last visit in Treatment period (evaluation at 52 weeks), all participants will be offered to continue with the treatment of darolutamide as long as they derived benefit, at the discretion of the investigator. All patients having been randomized to enzalutamide will be given the option to discontinue enzalutamide or offered to switch to treatment with darolutamide in this period.

For safety assessments, please refer to Section 8.7. The Sponsor reserves the right to terminate access to study intervention, in particular if the study is terminated due to safety concerns.

7. Discontinuation/Withdrawal Criteria

All participants who enter the study should complete all applicable study periods. Participants can be withdrawn from any study period at any time. Discontinuation of study treatment alone does not constitute withdrawal from the study.

Participants who discontinue the study treatment for any reason are to remain on the study for follow-up of primary, secondary and other objectives until week 52 (e.g., continue in the active follow-up periods, Table 1–5). Participants are expected to participate in active follow-up unless they explicitly object. Withdrawal of consent to the study treatment should be documented in the participant's medical record. If the participant does not wish to be followed up further, this additional consent withdrawal for follow-up must also be documented.

7.1 Discontinuation of Study Treatment

In some instances, it may be necessary for a participant to permanently discontinue (definitive discontinuation) study treatment (i.e., disease progression, unacceptable toxicity, study intervention interruption > 28 days, need for dose reduction below 300 mg bid). If study treatment is definitively discontinued, the participant is expected to participate in the active follow-up unless he explicitly objects. See the SoA (Section 1.5) for data to be collected at the time of intervention discontinuation and active follow-up and for any further evaluations that need to be completed. If the participant does not agree to active follow-up until week 52, he undergoes the EOT visit (within 30 days after last dose of study intervention).

If a clinically relevant finding is identified, including, but not limited to:

- Changes from baseline in QT interval corrected using Fridericia's formula (QTcF) after enrollment: the investigator or qualified designee will determine if the participant can continue in the study and if any change in participant management is needed. This review of the electrocardiogram (ECG) printed at the time of collection must be documented.
- Drug-induced liver injury (DILI): Participants who experience hepatic transaminase elevations suggestive of idiosyncratic drug induced liver injury (DILI) considered to be causally related to study intervention, should discontinue study intervention. (See appendix number 10.3.5).

Page: 51 of 86

Any new clinically relevant finding should be reported as an AE.

7.2 Withdrawal from the Study

A participant must be withdrawn from the study at any time at his own request.

A participant may be withdrawn from the study at any time at the discretion of the investigator for safety, behavioral, compliance, or administrative reasons and can do so (a) without giving reasons and (b) without suffering any disadvantages as a result.

If the participant withdraws consent for disclosure of future information, the Sponsor may retain and continue to use any data collected before such a withdrawal of consent.

If a participant withdraws from the study, and additionally requests destruction of his samples taken but not yet tested, the investigator must document this (either destruction by site or request to central lab, as applicable) in the site study records.

See the SoA (Section 1.5) for data to be collected at the time of study discontinuation and follow-up and for any further evaluations that need to be completed.

7.3 Lost to Follow-up

A participant will be considered lost to follow-up if he repeatedly fails to return for scheduled visits and is unable to be contacted by the study site.

The following actions must be taken if a participant fails to return to the clinic for a required study visit:

- The site must attempt to contact the participant and reschedule the missed visit* as soon as possible and counsel the participant on the importance of maintaining the assigned visit schedule and ascertain whether or not the participant wishes to and/or should continue in the study.
- Before a participant is deemed lost to follow up, the investigator or designee must make every effort to regain contact with the participant (where possible, 3 telephone calls and, if necessary, a certified letter to the participant's last known mailing address or local equivalent methods). These contact attempts should be documented in the participant's medical record.
- Should the participant continue to be unreachable, he will be considered lost to follow-up with a primary reason of lost to follow-up.

Discontinuation of specific sites or of the study as a whole are handled as part of the Appendices (Section 10.1.9).

*Note: Rescheduled visits may be performed using the remote visit option (see Section 8).

8. Study Assessments and Procedures

Study procedures and their timing are summarized in the SoA (Section 1.5).

Protocol waivers or exemptions are not allowed.

Immediate safety concerns should be discussed with the Sponsor immediately upon occurrence or awareness to determine if the participant should continue or discontinue study treatment.

Adherence to the study design requirements, including those specified in the SoA (Section 1.5), is essential and required for study conduct.

All screening evaluations must be completed and reviewed to confirm that potential participants meet all eligibility criteria. The investigator will maintain a screening log to record details of all participants screened and to confirm eligibility or record reasons for screening failure, as applicable.

Page: 52 of 86

Procedures conducted as part of the participant's routine clinical management (e.g., blood count) and obtained before signing of the informed consent form (ICF) may be utilized for screening or baseline purposes provided the procedures met the protocol-specified criteria and were performed within the time frame defined in the SoA (Section 1.5).

Note: If the study participant is not able to come to the investigational site for protocol specific visits, alternative methods for assessments (e.g., phone contact, virtual visit, alternative location for laboratory tests and imaging, provided that the imaging modality is consistent for a particular subject throughout the study) should be implemented when necessary and feasible as per local health authority and ethic committees. Darolutamide, typically distributed for self-administration, is also amenable to alternative secure delivery methods from the site pharmacy.

8.1 Imaging Time-Points

Radiological tumor assessments will be conducted only at screening to exclude presence of visceral metastases, and because these are not considered SOC, will only be done at other times based on treating physician discretion and/or based on PSA progression. Scans performed prior to the participant signing informed consent may be used for screening tumor assessments provided:

- CT/MRI/ PSMA-PET bone scans were conducted within 42 days prior to day 1 (D1)
- There has been no intervening therapy between the scans and D1

8.2 Serum Hormone Levels

Peripheral blood for measurement of serum hormone levels, including testosterone, free testosterone, DHT, DHEA, SHBG, androstenedione, prolactin, estradiol, LH, FSH and gonadotropins, will be collected. Collection of peripheral blood for measurement of serum hormone should coincide with fasting lipid panel. Refer to SoA (Section 1.5) for timing of sample collection.

8.3 PSA Measurement

For PSA response rate, serum PSA will be measured according to the study schedule (see SoA Section 1.5) using local laboratory's ultrasensitive assay. It is preferable that each subject has serial laboratory measurements of PSA at the same laboratory while on study.

Page: 53 of 86

8.4 Bone Health Assessment

DEXA scans, CTX and BSAP will be completed according to the study schedule (see SoA Section 1.5). The mean percent change in bone mineral density as measured at the spine, hip (total hip and femoral neck), and forearm (radius and ulna) will be compared between treatment arms.

8.5 Fasting Lipid Panel

The fasting lipid panel (total cholesterol, LDL, HDL, and triglycerides) will be measured according to the study schedules (see SoA Section 1.5). Subjects must be fasting for 9 to 12 hours prior to collection of blood for accurate measure of fasting lipid panel. If the subject is not in a fasting state at a particular study time point, the lipid panel will not be collected on that date and omitted from these exploratory statistical analyses.

8.6 Markers of Insulin Resistance

Fasting plasma glucose, fasting serum insulin, lean body mass, fat body mass and hemoglobin A1C will be measured according to the study schedules (See SoA Section 1.5). Subjects must be fasting for at least 8 hours prior to collection of blood for fasting glucose and insulin measurement. If the subject is not in a fasting state at the time point, the fasting glucose and insulin tests will be omitted from the analysis.

8.7 Safety Assessments

Planned time points for all safety assessments are provided in the SoA in Section 1.5.

Safety assessments in this study are AEs, as recorded by the investigator.

Changes in study visit schedules, missed visits, or participant discontinuations may lead to missing information (e.g., for protocol-specified procedures). The specific information (e.g., explanation of the basis of the missing data) will be captured in the case report form and the information will be summarized in the clinical study report. In all cases, existing regulatory requirements for maintaining investigational product accountability remain and should be addressed and documented.

Missing information will be recorded as protocol deviations and summarized in the Clinical Study Report.

The method of recording, evaluating, and assessing causality of AE and SAE and the procedures for completing and transmitting SAE reports are provided in Section 10.3.

The investigator and any qualified designees are responsible for detecting, documenting, and recording events that meet the definition of an AE or SAE and remain responsible for following up AEs that are serious, considered related to the study treatment or study procedures, or those that caused the participant to discontinue the study treatment (see Section 7).

QoL will be assessed with the FACT-P questionnaire (Section 10.4) during the visit, prior to any procedures or examination by physician.

8.7.1 Time Period and Frequency for Collecting AE and SAE Information

All AEs will be collected from the signing of the ICF until the EOT visit or end of active follow up.

Medical occurrences that begin before obtaining informed consent will be recorded on the medical history section of the case report form (CRF). Information on major diseases that have occurred in the study subject that might affect function of critical organs (e.g., renal failure, hepatic insufficiency, heart disease) should be collected at screening. Collection of additional clinical history or data that is considered related or appropriate information for study

Page: 54 of 86

intervention/disease under study or deemed relevant by the investigator should also be included.

Medical occurrences that begin before the start of study treatment but after obtaining informed consent will be recorded on the AE section of the case report form (CRF).

Medical occurrences that started before but deteriorated after obtaining informed consent will be recorded as AEs.

All SAEs will be recorded and reported to the Sponsor or designee within 24 hours if investigator awareness, as indicated in Appendix 3. The investigator will submit any updated SAE data to the Sponsor within 24 hours of it being available.

Investigators are not obligated to actively seek AE or SAE in former study participants. However, if the investigator learns of any SAE, including a death, at any time after a participant has been discharged from the study, and he considers the event to be reasonably related to the study treatment or study participation, the investigator must promptly notify the Sponsor.

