^a Radiological tumor assessments will be conducted only at screening to exclude presence of visceral metastases, and because these are not considered standard of care, will only be done at other times based on treating physician discretion and based on PSA progression. Investigators are encouraged to provide the results of PSMA-PET CT scans in the eCRF if performed (optional at baseline or during the study).

If patient treatment discontinued BEFORE completing the full 52-week treatment, please refer to the Active Follow Up Period SoA Table 1-5.

Bayer will provide questionnaires wherever validated version is available in the said language.

Abbreviations: A1C (hemoglobin) Glycated, AE adverse event, ALT Alanine aminotransferase, AST Aspartate aminotransferase, BSAP bone-specific alkaline phosphatase, CT computerized tomography, CTX C-terminal telopeptide, DEXA dual energy x-ray absorptiometry, DHEA dehydroepiandrosterone, DHT dihydrotestosterone, ECG Electrocardiogram, ECOG Eastern Cooperative Oncology Group, EOT end of treatment, FACT-P Functional Assessment of Cancer Therapy – Prostate Cancer, FSH-follicle-stimulating hormone, INR international normalized ratio, LH-luteinizing hormone, MRI magnetic resonance imaging, PC prostate cancer, PSA Prostate-specific antigen, PSMA-PET Prostate-specific membrane antigen positron emission tomography, PT prothrombin time, PTT partial thromboplastin time, SAE serious adverse event, SHBG sex hormone-binding globulin, SOC standard of care.

^b Safety assessments should be continued as per SOC at time of progression. After the 30-day short term follow-up period, only SAEs that are considered related to study intervention or study participation, with concomitant medications used to treat the event, should be reported by the investigator. Documentation of progression should be provided to the Sponsor (in CRF).

^c During the treatment period and up to 30 days following study intervention discontinuation, all (S)AEs are collected, regardless of causality.

^d For anti-cancer therapies, also collect prior to 28 days.

e Treatment compliance will also be assessed at each visit when study intervention is dispensed.

f Bioelectrical impedance scale to be used.

⁹ To be collected and updated as needed, not visit dependent. Eligibility assessments need to be completed prior to the patient being enrolled to the study.

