^h Tests related to inclusion exclusion criteria should be performed at screening visit. Neutrophil count, Platelet count, Total bilirubin, ALT, AST, Creatinine, Creatinine clearance, PTT, PT, INR. All the other clinical chemistry and hematology are mentioned in Section 10.2, Table 10-1.

¹ PROMIS, Self-Efficacy Assessment, and GODIN survey are not mandatory if translated version in not available. Questionnaires required are detailed in Section 10.4.

Assessment to be done in triplicate.

Page: 25 of 86

Table 1-5: Schedule of Activities Active Follow-up period

CTUDY ELEMENT/DEDIOD	Fau Dationto	ACTIVE FOLLOW UP PERIOD For Patients who discontinue treatment REFORE completing week 52 treatment for both Lead-in and Randomizer										
STUDY ELEMENT/PERIOD	For Patients who discontinue treatment BEFORE completing week 52 treatment for both Lead-in and Randomized Phases: Weeks											
VISIT (acceptable time window: days)	2 [± 7 d]	4 [± 7 d]	8 [± 7 d]	12 [± 7 d]	16 [± 7 d]	24 [± 7 d]	36 [± 7 d]	52 [± 7 d]				
Fasting glucose, fasting insulin, hemoglobin A1C, lipid profile, lean body mass ^a , fat mass ^a , weight		х		х		х	х	х				
Clinical chemistry (liver), hematology ^e		х		х		х	х	Х				
DHT, DHEA, SHBG, androstenedione, prolactin, estradiol		х		х		х	х	Х				
Vital signs		x		x		X	x	X				
Bone specific alkaline phosphatase (BSAP) and CTX		х		х		х	х	Х				
Efficacy												
Testosterone, free testosterone	Х	х	X	X	X	X	X	X				
Serum PSA	Х	х	X	x	x	X	x	X				
Gonadotropins, LH, FSH	х	х	Х	х	х	Х	х	Х				
24 DEXA scan								Х				
Patient reported outcomes												
FACT-P		х		х		Х	х	Х				
Surveys: physical function ^b				х		Х		Х				
Safety												
AE/SAE assessment ^c					Xd							

^a Bioelectrical impedance scale to be used.

Bayer will provide questionnaires wherever validated version is available in the said language.

Abbreviations: A1C (hemoglobin) Glycated, AE adverse event, ALT Alanine aminotransferase, AST Aspartate aminotransferase, BSAP bone-specific alkaline phosphatase, CT computerized tomography, CTX C-telopeptide, DEXA dual energy x-ray absorptiometry, DHEA dehydroepiandrosterone, DHT dihydrotestosterone, FACT-P Functional Assessment of Cancer Therapy – Prostate Cancer, FSH follicle-stimulating hormone, INR international normalized ratio, LH-luteinizing hormone, PSA Prostate-specific antigen, PT prothrombin time, PTT partial thromboplastin time, SAE serious adverse event, SHBG sex hormone-binding globulin.

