^b PROMIS, Self-Efficacy Assessment, and GODIN survey are not mandatory if translated version in not available.

^c Concomitant medications used to treat related AEs that were unresolved at EOT will be capture in Active Follow-up period.

^d To be collected and updated as needed, not visit dependent.

e Tests related to inclusion exclusion criteria should be performed at screening visit. Neutrophil count, Platelet count, Total bilirubin, ALT, AST, Creatinine, Creatinine clearance, PTT, PT, INR. All the other clinical chemistry and hematology are mentioned in Section 10.2, Table 10-1.

Page: 26 of 86

2. Introduction

Darolutamide is a next-generation nonsteroidal androgen receptor inhibitor (ARI) for the treatment of prostate cancer, which binds with a high affinity and selectivity to the androgen receptor (AR) with potent and improved antagonism for AR.

Darolutamide has shown a very low blood-brain barrier penetration in rodents (Zurth et al. 2019) compared to enzalutamide and apalutamide. First data in humans also suggest that darolutamide has a favorable impact on brain blood flow compared to enzalutamide and that this might be attributable to difference in blood brain barrier penetration (BBB). Differences in BBB penetration of treatment and therefore, the effect on the central nervous system (CNS) may reduce the risk of CNS related side effects such as cognitive function, fatigue falls, dizziness, and depressed mood disorders.

Darolutamide plus androgen deprivation therapy (ADT) demonstrated significant improvement of metastasis-free survival (MFS) and overall survival (OS) in patients with non-metastatic castration resistant prostate cancer (nmCRPC) compared to ADT alone in the phase III ARAMIS study (Fizazi et al. 2019). The primary analysis in ARAMIS showed a median MFS improvement of 22 months (40.4 months in darolutamide compared with to 18.4 months in placebo arms HR of 0.41; 95% CI 0.34 to 0.50).

The final analysis showed a statistically significant benefit in overall survival (HR 0.69; 95% CI 0.53 to 0.88) and all other secondary end points such as time to pain progression, time to cytotoxic chemotherapy, and time to a symptomatic skeletal event.

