4.5.2 Adverse Events

Treatment-emergent AE (TEAE) is defined as any event arising or worsening after the first dose of study drug until 30 days after the last dose of study drug.

An overview of TEAEs will be summarized for the appropriate safety analysis set at the three data cuts. The following summaries will be done.

- Overview of TEAEs
- TEAEs by MedDRA ad worst CTCAE grade
- TEAEs by MedDRA ad worst CTCAE grade 3, 4 or 5
- TEAEs: number of subjects by primary SOC and PT
- TEAEs leading to permanent discontinuation of study drug: number of subjects by primary SOC and PT
- Number of subjects with TEAE by PT in decreasing order
- Drug-related TEAEs: number of subjects by primary SOC and PT

• Drug-related TEAEs leading to permanent discontinuation of study drug: number of subjects by primary SOC and PT

Page: 18 of 31

- Number of subjects with drug-related TEAE by PT in decreasing order
- SAEs: number of subjects by primary SOC and PT
- TESAEs: number of subjects by primary SOC and PT
- Drug-related TESAEs: number of subjects by primary SOC and PT
- TE non-SAEs (excluding TESAEs): number of subjects by primary SOC and PT

Additionally, feminizing side effects as described in Section 4.3, will be summarized by

- Overview of TEAEs of feminizing side effects
- Number of subjects with TEAEs of feminizing side effects by PT in decreasing order
- Treatment-emergent study drug-related adverse events of feminizing side effects by MedDRA SOC and PT and worst CTCAE grade
- Number of subjects with TEAEs of feminizing side effects leading to permanent discontinuation of study drug by PT in decreasing order
- Number of subjects with drug-related TEAEs of feminizing side effects by PT in decreasing order
- Number of subjects with drug-related TEAEs of feminizing side effects leading to permanent discontinuation of study drug by PT in decreasing order
- SAEs of feminizing side effects: number of subjects by primary SOC and PT
- TESAEs of feminizing side effects: number of subjects by primary SOC and PT
- Drug-related TESAEs of feminizing side effects: number of subjects by primary SOC and PT

AEs of special topics will be summarized by

• Number of subjects with special topics for adverse events

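### For men who stop treatment early and enter active follow-up, the protocol gives two AE collection rules beyond 30 days after last dose and does not say which prevails

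*Protocol*

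**What the plan says.** Protocol 8.7.1 sets the collection period: "All AEs will be collected from the signing of the ICF until the EOT visit or end of active follow up". It does not say which of the two end points applies to whom. The same section has all SAEs recorded and reported within 24 hours. It brings in relatedness only for SAEs that the investigator learns of after a participant has been discharged from the study.

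The schedules in Section 1.5 add three further texts.

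- Footnote c of Tables 1-3 and 1-4: "During the treatment period and up to 30 days following study intervention discontinuation, all (S)AEs are collected, regardless of causality".
- Footnote b of the same tables, attached to their AE/SAE row: "After the 30-day short term follow-up period, only SAEs that are considered related to study intervention or study participation" are to be reported. It opens by referring to the time of progression.
- Table 1-5, the active follow-up schedule, has a row headed "AE/SAE assessment", annotated "To be collected and updated as needed, not visit dependent". It has no restriction to serious or related events.

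A routing sentence sits under Tables 1-3 and 1-4: "If patient treatment discontinued BEFORE completing the full 52-week treatment, please refer to the Active Follow Up Period SoA Table 1-5". Under Protocol 4.1.3, active follow-up runs to week 52.

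SAP 4.5.2 ends the treatment-emergent period 30 days after last dose. Among its outputs it lists "SAEs: number of subjects by primary SOC and PT" and a matching table for feminizing side effects, each separate from its treatment-emergent counterpart.

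**The concern.** A man who stops treatment early has not left the study. Protocol Section 7 says that stopping treatment alone is not withdrawal, and it keeps him under assessment to week 52. Under 8.7.1 and Table 1-5, a site records every AE during that time. Under footnotes b and c, a site records only SAEs judged related once 30 days have passed. Two sites could each follow the protocol and send in different data.

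Under the footnote rule, an investigator who knows the treatment decides by a causality call whether a late SAE is recorded at all. An event that was never collected may not be recoverable at analysis. Safety is a secondary objective in both phases, so the collection window should not depend on which page a site reads.

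**Working it through.** The plan states no figure on this point, so there is none to reproduce. The check compares the texts, measures the period in dispute, and traces it into the SAP outputs.

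**Step 1: the rules side by side, for a man in active follow-up more than 30 days after last dose**

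| Text | Non-serious AE | Unrelated SAE | Related SAE |
|---|---|---|---|
| 8.7.1, read to the end of active follow-up | collected | collected | collected |
| Table 1-5 AE/SAE row | collected | collected | collected |
| Tables 1-3 and 1-4, footnotes b and c | not collected | not collected | collected |

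The texts agree up to day 30, and they agree on related SAEs after it. They disagree on unrelated SAEs and on all non-serious AEs.

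**Step 2: length of the disputed period**

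Inputs: active follow-up ends at week 52 (Protocol 4.1.3), and the footnotes change the rule 30 days after discontinuation. For a last dose at week *w*, using nominal dates:

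disputed days = (52 − *w*) × 7 − 30

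- *w* = 4: 48 × 7 − 30 = 306
- *w* = 12: 40 × 7 − 30 = 250
- *w* = 24: 28 × 7 − 30 = 166
- *w* = 36: 16 × 7 − 30 = 82
- Zero when 52 − *w* = 30/7 = 4.3, so *w* is about 47.7

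Men who complete 52 weeks are almost unaffected. Their EOT visit falls 30 to 37 days after last dose, so the texts differ by at most 7 days.

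**Step 3: which planned outputs can change (SAP 4.5.2)**

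- All tables of treatment-emergent events, serious or not: no change, because they stop at 30 days after last dose.
- Feminizing side effects: every table but one is treatment-emergent and does not change. SAP 4.1.1 also frames both primary analyses in terms of treatment-emergent events. The exception is the table of feminizing SAEs.
- The overall SAE table and the feminizing SAE table, neither limited to treatment-emergent events: these can change through a late SAE judged unrelated.
- The special-topics table: it is not labelled treatment-emergent, and its topics in SAP 4.3.1.1 include falls, fatigue, fractures and breast disorders. It could change through late events, including non-serious ones, if it is programmed without the 30-day cut. The SAP does not settle this.

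**The case against.** The strongest reply is that the routing sentence resolves the matter. On that reading, footnotes b and c belong to Tables 1-3 and 1-4, which end at the EOT visit, and Table 1-5 alone governs early stoppers. The two end points in 8.7.1 then fall into place: the EOT visit for completers and for men who decline active follow-up (Protocol 7.1), and the end of active follow-up for the rest. For men who have finished the study, footnote b agrees with the post-discharge rule in 8.7.1.

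This is a coherent reading, and it narrows the conflict. It does not remove it. Footnote c speaks of discontinuation of the study intervention and footnote b of progression, which Protocol 7.1 lists as a reason to stop. Neither is limited to men outside active follow-up. The concomitant-medication rules in Table 1-5 footnote c and Protocol 6.7 are also confined to related events (6.7 adds antineoplastic therapy), which fits the narrower collection rule. No text gives precedence.

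The reply also notes, correctly, that all safety analyses are descriptive, that the separate treatment-emergent SAE table gives a comparison unaffected by the conflict, and that neither the primary endpoint nor the 45% testosterone condition is touched.

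A reader might infer that feminizing-effect counts become non-comparable between arms. The documents do not support that. Those counts are almost all cut at 30 days, and a non-serious gynecomastia event cannot enter the one exception, which is an SAE table.

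**Conclusion.** The inconsistency is real, stands in current text, and should be corrected. Its reach is limited to events starting more than 30 days after last dose in men who stopped before about week 48 and remained in active follow-up. For those men, whether unrelated SAEs and non-serious AEs are collected depends on which text the site follows. The affected outputs are the two SAE tables not limited to treatment-emergent events and possibly the special-topics table.

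The 306, 250, 166 and 82 days are illustrations at assumed stopping times. The documents give neither the number of men who will enter active follow-up nor a rate of late events, so no expected number of affected events can be stated. A reader might take the gap between 40 randomized and 34 evaluable as the number affected. It is not: evaluability rests on baseline and week 12 testosterone and on eligibility. A man who stops at week 20 can be evaluable, and a man lost to follow-up never enters active follow-up. Nor do the documents show that sites will in fact differ; they only permit it.

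**What to change.** In the protocol, reconcile 8.7.1, footnotes b and c of Tables 1-3 and 1-4, and Table 1-5 to one collection window for men in active follow-up. The 8.7.1 rule fits the visits already scheduled in Table 1-5. State in 8.7.1 who stops at the EOT visit and who continues to the end of active follow-up. Check that the concomitant-medication wording in 6.7 and Table 1-5 footnote c agrees with the chosen window.

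In SAP 4.5.2, report events with onset more than 30 days after last dose separately from treatment-emergent events, and say whether the special-topics table is limited to treatment-emergent events.

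The cost is footnote and section wording, slightly more AE data entry for men in active follow-up, and one extra table split.
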